## 4 STUDY DESIGN

### 4.1 OVERALL DESIGN

This is a double-blind, placebo-controlled, randomized phase 2 study evaluating the combination of zinc citrate, green tea extract, and ascorbic acid supplementation given for five days on reduction in symptom duration and severity associated with an acute community respiratory viral infection, including COVID-19. Patients presenting to MUHC emergency department (ED) seeking routine care for respiratory viral illness related symptoms will be screened for study eligibility by ED medical staff. A target of 100 eligible patients will be consented and enrolled into the trial by key study personnel in the ED at the time of their visit. A study prescription will be generated by an authorized study team member also at the time of visit and will be sent to the MUHC investigational research pharmacist or designated pharmacist for processing. This will include 1:1 randomization of the study subject to one of the two study arms (n=50 for each arm), filling of prescription with required documentation and labeling, and coordination with ED research services for final dispensing to the patient. Study patients will be discharged from the ED with their study drug before returning home later that day. Due to the time sensitive inclusion criterion necessitating same day study drug dispensing patients seeking medical care

during normal business hours (Monday – Friday; 0800 – 1630) will be targeted for enrollment, however, after hours enrollment may occur based on availability of investigational drug services pharmacy staff or designated pharmacist. Use of a placebo control and treatment blinding is required to limit observer and recall bias given the subjectivity of the outcomes of measure. Patients enrolled will be instructed to discontinue any current OTC products that contain any of the components of the study drug to mitigate confounding of treatment effect. Common cough and cold products that do not share ingredients with study drug will be allowed, and daily utilization will be quantified as name and number of products used and doses of each taken daily. This strategy will allow standard-of-care treatment via patient directed symptom management using traditional OTC cough and cold medicines, while minimizing bias in evaluation of study outcomes. Placebo assignment is assessed to be ethical as no FDA approved therapy for the prevention or treatment of non-influenza respiratory viral illness exists.

A separate study is planned that will collect blood samples in 10 patients to assess serum concentrations of zinc and EGCG, and a complete metabolic panel (CMP) following five days of taking study drug. Baseline serum zinc levels will be collected at time of study enrollment in the MUHC ED while post-treatment serum concentrations of zinc and EGCG will be obtained on the fifth day of taking study drug. Patients will be instructed to report to the MUHC emergency department approximately two hours following taking a dose of study drug to have their blood drawn for the aforementioned testing. CMP assays will be processed locally at MUHC while serum zinc samples will be sent to Mayo Clinic, and EGCG samples will be sent to the University of Missouri Metabolomics Center for analysis. Patients will be selected using the same criteria as those enrolled in the placebo-controlled trial, but will not be randomized to blinded treatment given the logistical requirements necessitating accurate blood sampling. These patients will also not be a part of primary and secondary endpoint collection via daily telephone visits. The purpose of this study is to simply describe peak serum levels of zinc and EGCG following multiple dosing of the study drug, as well as to assess the rate of transaminitis if any is to occur. A separate consent form will be used for this aspect of the research.

#### 4.2 SCIENTIFIC RATIONALE FOR STUDY DESIGN

No oral drug therapy or dietary supplement has been FDA approved for the prevention or reduction in symptom duration of non-influenza viral respiratory illness including the ‘common cold’ and COVID-19. Recently the FDA authorized use of newer therapies for COVID-19 in non-hospitalized patients including nirmatrelvir-ritonavir and molnupiravir, however, these are recommended for those only at high risk of progressing to severe disease leaving many healthier patients without options for disease management. Since no established FDA approved standard-of-care currently exists a placebo-controlled trial presents little to no ethical challenge. Furthermore, the primary and secondary outcomes are self-reported measures by study participants and the subjectivity of these endpoints necessitates a placebo group for statistical comparisons that minimize recall and observer bias.

#### 4.3 JUSTIFICATION FOR DOSE

##### Zinc Citrate

Zinc is an essential trace element with a wide therapeutic index, and deficiency is common in developing nations and in the elderly (normal range: 10 - 16.8  $\mu$ M). Zinc deficiency has been associated with

increased pneumonia risk, and supplemental doses greater than 75 mg/day have been associated with a reduction in the duration of the common cold. A total daily dose of elemental zinc up to 207mg given for seven days has been studied in adults with common cold, and doses ranging between 100 to 150 mg/day have been administered for months at a time for other indications with few adverse effects reported. A recent study specifically evaluating zinc lozenges (78mg elemental zinc/day) administered for five days for common cold reported side effects of taste disturbances (52%) and dry or sore mouth (24%) that occurred at a greater rate than placebo (7% and 2%, respectively). However, no serious events were reported.

The dose of zinc selected for this study is based on a pharmacokinetic evaluation of serum zinc concentrations over time following oral administration of 45mg elemental zinc provided as gluconate given under fasting, with food, and two hours post meal conditions in ten young healthy volunteers, 23  $\pm$  2 years (mean  $\pm$  SD) with an average weight of 70  $\pm$  8 kgs. This dose of zinc was able to raise the serum concentration (Cmax) by 2.45  $\mu$ M from baseline (11  $\pm$  2  $\mu$ M) when administered two hours after a meal, while no appreciable increase was observed when zinc was administered with food. The selected dose of elemental zinc given as citrate (33 mg/capsule) for the current study is anticipated to raise serum concentrations (Cmax) in a similar fashion and in a dose proportional manner whereby a  $\sim$ 5  $\mu$ M increase is expected with a doubling of the dose (i.e. 100mg vs 45mg). The 5  $\mu$ M increase in Cmax is desired as the ability of EGCG to raise intracellular zinc levels appears to be dependent on the extracellular zinc concentration. Unpublished in-vitro data have demonstrated 10  $\mu$ M zinc necessitating higher concentrations of EGCG to significantly elevate intracellular zinc (figure 2, unpublished data). Assuming patients enrolled have a serum zinc concentration near 10  $\mu$ M at baseline (based on studies in healthy volunteers and those with viral respiratory disease), a higher dose of zinc would be required to achieve serum levels (Cmax) near 20  $\mu$ M. This higher extracellular zinc concentration would allow for lower concentrations of EGCG to significantly increase intracellular zinc (figure 1, unpublished data), which is desirable given the relatively poor bioavailability of orally administered EGCG. Although zinc gluconate was the form of zinc utilized for pharmacokinetic study, zinc citrate has been demonstrated to display similar characteristics as zinc gluconate in healthy volunteers with comparable bioavailability (61.3% vs 60.9%, respectively).

Zinc toxicity has been rarely reported, but ingestion of 10 - 30 grams of zinc sulfate (2.5 - 7.5 grams of elemental zinc) can be lethal in adults. Chronic intake of 450 - 1600mg daily can cause anemia, copper deficiency, and myeloneuropathies. Total daily exposure of zinc used in the current study proposal is well below these harmful doses and will be limited to five days in duration. Additionally, twice daily dosing would not be expected to lead to systemic accumulation as the elimination half-life of orally administered zinc is 1.1 hours. Elimination of zinc is mostly through the feces therefore renal impairment would not be expected to alter clearance.

#### Green Tea Extract

EGCG is a polyphenolic compound found predominately in green tea (*Camellia sinensis*), but is also found in other foods including a variety of fruits and nuts albeit in smaller amounts. A 250 mL cup of brewed green tea contains approximately 25 - 60mg of EGCG along with variable amounts of caffeine. Green tea extract is often sold as a dietary supplement containing 50% or more of EGCG by weight and contains little to no caffeine allowing for higher dosing of the antioxidant catechin compounds found in whole plant tea drinks. EGCG displays a wide therapeutic index with doses studied ranging from 150 -

2,400 mg in subjects without serious adverse effects. EGCG is metabolized via methylation by catechol-O-methyltransferase (COMT) as well as degradation by colonic bacteria with metabolites excreted through both urinary and fecal routes. Drug interaction studies have indicated that EGCG is not expected to inhibit the CYP enzymes 1A2, 2D6, 2C9, or 3A4 to any clinically significant degree following repeated doses of 800 mg/day.

Study dosing of EGCG was selected based on published pharmacokinetic data detailing serum concentrations over time following single and multiple doses of 400mg twice daily in healthy volunteers. A single dose of 400mg taken with food corresponded to an average EGCG Cmax of  $0.38 \pm 0.18 \mu\text{M}$ , while fasting conditions yielded a mean Cmax of  $1.65 \pm 0.87 \mu\text{M}$  in healthy volunteers (average age of 42 years and weight of  $75 \pm 20 \text{ kgs}$ ). A multiple dose study evaluating 400mg twice daily taken with food for four weeks demonstrated a mean Cmax of  $0.34 \pm 0.14 \mu\text{M}$  in a separate but similar volunteer population indicating little to no accumulation with this dosing schedule. These serum concentrations were simulated in-vitro to establish a dose response curve of EGCG to increase intracellular zinc concentrations (figure 1, unpublished data). Results indicate the ability of obtainable concentrations of EGCG from a dosing schedule of 400mg twice daily to significantly increase intracellular zinc levels in human kidney cells under experimental conditions. The current study proposal will evaluate the effect of this activity in-vivo providing translational evidence for combination supplementation to improve immune health during an acute respiratory viral illness.

Safety and toxicity data on EGCG have been thoroughly summarized by formal drug safety panels including the European Food and Safety Authority (EFSA) and United States Pharmacopeia Convention (USP). Common mild side effects reported with standard dosing include gastrointestinal symptoms especially when taken in a fasting state, but rare cases of hepatotoxicity have been reported. The EFSA and USP concluded that doses equal to or greater than 800mg of EGCG per day taken for four months or longer are associated with elevations of alanine aminotransferase (ALT) and aspartate transaminase (AST) in a small percentage (less than 10%) of the population. The strongest evidence for safety and hepatotoxicity risk of EGCG comes from the Minnesota Green Tea Trial (MGTT). This was a randomized, placebo-controlled, double-blind trial investigating the effects of daily EGCG (843 mg/day) for 12 months in 1075 post-menopausal women. 538 subjects were randomized to EGCG and the difference in biomarkers for the development of breast cancer was compared against placebo (n=537). The most common side effect reported that occurred significantly more often than placebo was nausea (10.2% vs 4.8%, p =0.001), while no differences were seen in rates of serious adverse events (2.2% vs 1.5%). Liver enzyme elevations in patients taking EGCG occurred more frequently compared to placebo (6.7% vs 0.7%, p < 0.001), however, the average increase in ALT was only 5.4 U/L and was reversible after stopping therapy. Overall, green tea extracts are generally considered safe for human consumption with liver injury occurring rarely with doses less than or equal to 800 mg/day of EGCG and taken less than two weeks in duration.

#### Ascorbic Acid

Vitamin C is an essential nutrient for human health and must be obtained through dietary supplementation. Clinical uses of ascorbic acid include treatment of scurvy, enhancing absorption of iron, acidification of urine, skin care, and prevention and treatment of the common cold. Although the immunomodulatory properties of vitamin C are favorable the purpose for the proposed study is to enhance absorption of EGCG. This is achieved by combining 200mg of ascorbic acid with

standard and high doses of EGCG, which has been previously described. Safe dosing of vitamin C has been established up to 2000 mg/day where higher doses are associated with diarrhea and gastrointestinal upset. Total daily exposure with the designed dosing protocol (400mg) is well below the recommended daily limit and thus no serious adverse effects are expected.

#### 4.4 END OF STUDY DEFINITION

The end of the study is defined as completion of the last visit or procedure shown in the SoA in the trial globally. The study period will be terminated early if the IRB, Independent Safety Monitor, or study investigators determine that the study jeopardizes patient safety beyond an expected risk level at any time.

### 5 STUDY POPULATION

#### 5.1 INCLUSION CRITERIA

In order to be eligible to participate in this study, an individual must meet all of the following criteria:

1. Provision of signed and dated informed consent form
2. Stated willingness to comply with all study procedures and availability for the duration of the study
3. Male or female, aged 18 years and older
4. Ability to take oral medication and be willing to adhere to the prescribed dosing regimen
5. Self-reported cold or flu symptoms for < 72 hours

Men and women of all ethnicities will be included.

#### 5.2 EXCLUSION CRITERIA

An individual who meets any of the following criteria will be excluded from participation in this study:

1. Pregnant or actively seeking to become pregnant
2. Positive for influenza with planned treatment with oseltamivir or baloxavir
3. Current or planned treatment with an FDA regulated drug (including those under EUA) for COVID-19
4. Chronic liver disease (i.e. baseline liver function tests (LFTs) > 1.5x the ULN or established cirrhosis)
5. Chronic renal failure stage 4 or greater
6. History of kidney stones
7. Acute secondary bacterial infection at the time of enrollment
8. Requiring hospitalization for any reason at the time of enrollment
9. History of copper or iron deficiency
10. Current prescription for quinolone antibiotics, tetracycline antibiotics, or penicillamine at the time of enrollment

11. Allergy/intolerance to any of the active ingredients under investigation including zinc citrate, green tea extract, and ascorbic acid (vitamin C)
12. Patients without decision making capacity
13. Currently enrolled in another clinical trial for a respiratory viral infection

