## 6 STUDY INTERVENTION

### 6.1 STUDY INTERVENTION(S) ADMINISTRATION

#### 6.1.1 STUDY INTERVENTION DESCRIPTION

The compounded supplementation study product includes select amounts of zinc citrate, green tea extract, and ascorbic acid that have been mixed together using geometric dilution to form a light brown fine powder, and is capsulated using a capsule machine with size 0 empty gelatin capsules resulting in a measured weight of  $438\text{mg} \pm 10\%$  per capsule. The per capsule amount of each supplement component is as follows:

267mg of green tea extract/capsule  
104mg of zinc citrate (33mg elemental zinc)/capsule  
67mg ascorbic acid/capsule

The finished goods specification sheets, safety data sheets, and certificate of analysis (CoA) for each respective supplement has been provided by the supplier and have been attached as addendums.

Addendum A – zinc citrate specification sheet, safety data sheet, and CoA  
Addendum B – green tea extract ( $\geq 50\%$  EGCG) specification sheet, safety data sheet, and CoA  
Addendum C – ascorbic acid specification sheet, safety data sheet, and CoA

Zinc citrate is a white crystalline powder containing 32% zinc by weight. Zinc is a naturally occurring element that is essential for human health, and various salts are available over-the-counter (OTC) for supplementation purposes. The FDA approved zinc product is zinc sulfate for injection.

Green tea extract is a brown powder-like substance derived from the stems and leaves of *Camellia sinensis* through an extraction process using water and organic solvents such as ethanol. A variety of green tea extracts are available over-the-counter for supplementation and contain little to no caffeine. Extract products contain high amounts of antioxidant catechin compounds the most abundant of which is epigallocatechin-3-gallate (EGCG). The EGCG content of most available green tea extract products is 50% by weight, but variability exists due to inconsistencies in manufacturing processes. The FDA approved a green tea extract product in 2006 called Veregen® (sinecatechins) ointment, which was the first prescription botanical accepted by the governing body.

Ascorbic Acid commonly known as vitamin C is available as a white crystalline powder and available over-the counter for oral supplementation. It is an essential nutrient naturally found in food sources and is FDA approved for the treatment of scurvy.

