Placebo capsules will be filled with microcrystalline cellulose, which is refined wood pulp commonly used in food production as an anti-caking or bulking agent. It is a chemically inert compound with no appreciable absorption following oral administration, and has been rarely reported to induce an allergic reaction. The per capsule amount of microcrystalline cellulose is as follows:

300mg ± 10% of microcrystalline cellulose/capsule

The certificate of analysis for microcrystalline cellulose is attached as an addendum.

Addendum D - microcrystalline cellulose CoA

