#### 6.1.2 DOSING AND ADMINISTRATION

Eligible patients will be randomized 1:1 to one of the following treatment groups with the following dosing schedule:

1. Zinc/EGCG/ascorbic acid blend: three (3) capsules taken orally two (2) hours following a meal twice daily x5 days.
2. Placebo: three (3) capsules taken orally two (2) hours following a meal twice daily x5 days

The per capsule and total daily dose of each of the individual supplement components is as follows:

267mg green tea extract/capsule (1,600 mg/day)  
33mg elemental zinc/capsule (200 mg/day)  
67mg ascorbic acid/capsule (400 mg/day)

The per capsule and total daily dose of each of the placebo component is as follows:

300mg microcrystalline cellulose/capsule (1,800 mg/day)

Patients will be instructed to begin taking their assigned study product starting the evening of enrollment day and to continue for five consecutive days. For missed doses study participants will be instructed not to double up on doses and to take the prescribed dose at the next scheduled administration time. Study product should be stored away from children so to avoid unintended administration by unauthorized study participants.

Study participants who will be undergoing blood sampling procedures will not be randomized or receive placebo.

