#### 6.2.2 FORMULATION, APPEARANCE, PACKAGING, AND LABELING

Study products will be prepared using University of Missouri Health Care (MUHC) pharmacy compounding resources using traditional practices of geometric dilution and capsulation. Compounding and dispensing of study supplement and placebo will be in compliance with Missouri Board of Pharmacy regulation 20 CSR 2220.2.400 Compounding Standards of Practice. White, opaque size 0 gelatin capsules will be used to prepare both study supplement and placebo, and will be dispensed into amber prescription bottles with tamper resistant tops for patient delivery. Labeling of study product will be in such a way to maintain blinding, but will include all information as required by state and federal regulations including: 1) The date the prescription was filled; 2) A prescription number or other unique identifier; 3) The patient's name; 4) The prescriber's directions for use; 5) The prescriber's name; 6) The pharmacy/institution's name, address, and contact information; 7) blinded name of study drug dispensed. The Federal Investigational Drug Caution Statement—"CAUTION: Drug limited by Federal (United States) Law to investigational use only."—will be applied to the study drug products.

---

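### Exclusion 11 bars allergy only to the active ingredients, so a known allergy to the placebo filler does not bar entry

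*Combined protocol and SAP*

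**What the plan says.** Exclusion 11 in section 5.2 reads: "Allergy/intolerance to any of the active ingredients under investigation including zinc citrate, green tea extract, and ascorbic acid (vitamin C". The three substances listed are the complete set of actives.

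Section 6.1.1 describes the comparator: "Placebo capsules will be filled with microcrystalline cellulose". The same paragraph calls this material inert and essentially unabsorbed, and adds that it "has been rarely reported to induce an allergic reaction". Section 6.1.2 gives the amount as "300mg microcrystalline cellulose/capsule (1,800 mg/day"), and on allocation says "Eligible patients will be randomized 1:1 to one of the following treatment groups".

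On the shell, section 6.2.2 says "White, opaque size 0 gelatin capsules will be used to prepare both study supplement and placebo". The shell is therefore common to both arms.

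**The concern.** Section 6.1.1 records a possible allergic hazard from the filler, and section 5.2 does not carry it into the eligibility rules. Section 8.1 has eligibility judged against the protocol's inclusion and exclusion criteria, and section 4.1 has patients consented, randomized and given study drug during the same emergency department visit. Someone who mentions a known allergy to microcrystalline cellulose meets no written exclusion.

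What is at stake is mainly participant safety: exposure to a known personal allergen that one line of screening could avoid. A minor consequence is that allergic reaction is a solicited event (sections 8.2 and 8.3.4) and is included in the adverse-event comparison with placebo (sections 9.1 and 9.4.3). A filler reaction would therefore enter the trial's data as a placebo-arm event.

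**Working it through.** The plan gives no figure for this risk, so there is nothing to reproduce. The check compares the criteria with the product description, followed by simple arithmetic on exposure and on the largest possible effect.

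**Step 1: does any criterion cover the filler?**

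- Exclusion 11 is confined to active ingredients. Microcrystalline cellulose is not one of them.
- The other 12 exclusions in section 5.2 concern pregnancy, influenza and COVID-19 treatment, liver and kidney conditions, bacterial infection, hospitalization, copper or iron deficiency, named prescriptions, decision-making capacity and other trials. None mentions excipients or placebo content, and none leaves entry to the investigator's discretion.
- Of the five inclusion criteria in section 5.1, the nearest is "Ability to take oral medication and be willing to adhere to the prescribed dosing regimen". It does not address allergy.
- Section 7.2 allows withdrawal of a participant found to meet an exclusion criterion. A filler allergy is not an exclusion criterion, so that route does not apply either.

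Result: the filler is not covered.

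**Step 2: who is exposed, and to how much?**

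- Sections 4.1 and 9.2 plan 100 participants, 50 per arm, so 50/100 = half receive the filler.
- Capsules over the full course (section 6.1.2): 3 per dose × 2 doses per day × 5 days = 30.
- Filler per day: 300 mg × 6 capsules = 1,800 mg, which matches the protocol's own figure.
- Filler over the full course: 1,800 mg × 5 days = 9,000 mg = 9 g.
- The 10 patients in the separate blood-sampling study are chosen by the same criteria (section 4.1) but receive no placebo (section 6.1.2), so the filler gap does not reach them.

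**Step 3: the largest effect on the adverse-event comparison.**

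Section 9.4.3 tests adverse events as one combined yes/no endpoint per participant. One extra placebo participant with an event moves that arm's rate by 1/50 = 2 percentage points. This is a ceiling: if the same person also reports nausea, vomiting, indigestion or another listed event, the combined endpoint is already positive and the shift is zero.

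**Step 4: how many participants might be affected?**

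Let q be the proportion of enrolled participants with a known filler allergy who would react. The documents give no value for q. The expected number of reactions on placebo is 50 × q. It reaches one only if q = 1/50 = 2%, which is hard to square with a reaction the protocol calls rare. For any q consistent with that word, the expected number is near zero.

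**The case against.** The strongest reply is that there is no contradiction to resolve. Section 6.1.1 presents the filler as inert, essentially unabsorbed and common in food, and an allergy exclusion limited to the substances under investigation fits that assessment. There are other safeguards too. A physician screens the patient and takes a history (sections 8.1 and 8.2), and an authorized prescriber and a pharmacist handle the study prescription (section 6.2.1). The consent forms, which are separate documents not available here, may carry a warning (section 10.1.1.1). Allergic symptoms are asked about daily (section 8.2), and emergency unblinding is available at all hours (section 6.3).

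Much of this stands. The sections do not conflict, and the safeguards make an actual reaction less likely or would catch it early. None of them is an eligibility criterion, however. They depend on someone going beyond the written rule, or they act after exposure. The omission remains, with small practical weight.

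A reader might infer two stronger points that the documents do not support:

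- **That the gap biases the safety comparison in favor of the supplement.** A filler reaction could indeed arise only on placebo. But the tested endpoint is a composite, the 2-point shift is the maximum for any single placebo event, and the rewording would prevent only reactions in people who already know of the allergy. First-time reactions would still occur and still count.
- **That gelatin allergy is an equally documented hazard.** The documents mention gelatin only as shell material and nowhere call it an allergen. As both arms use the same shell, it would in any case give no directional effect.

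**Conclusion.** The point holds as a small gap in the eligibility criteria: as written, a known allergy to microcrystalline cellulose does not prevent randomization, although the protocol acknowledges that allergic reactions to it have been reported. Closing the gap is a modest gain in participant safety for a rare situation.

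Statistically it is close to negligible. The ceiling is 2 percentage points on the combined adverse-event rate per placebo-arm event, and the expected effect is near zero. It gives no ground for doubting the trial's conclusions. This rests on the planned 50 per arm, on the composite definition in section 9.4.3, and on taking the protocol's description of such reactions as rare at face value, since it gives no rate. The consent forms could not be checked, but a warning there would not amount to an exclusion.

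**What to change.** Reword exclusion 11 to cover allergy or intolerance to any component of the active or placebo capsules, including zinc citrate, green tea extract, ascorbic acid and microcrystalline cellulose. This general wording also takes in the gelatin shell without the protocol having to make a separate claim about gelatin. If any screening or consent material repeats exclusion 11, it should carry the same words; the documents show no screening checklist, so this applies only where such material exists.

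The cost is one phrase, which can go into the next amendment with the usual IRB review. The loss of eligible patients would be negligible. Randomization, sample size, endpoints and analysis are unchanged.
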